Response (CR/iCR/PR/iPR) duration	Duration of response will be analyzed for patients who reach at least PR/iPR at any time during the study using Kaplan-Meier methods. A responding patient who experiences any form of progression will be evaluated as a patient with event. The starting point is the first diagnosis of CR/iCR or PR/iPR. The time point of the event will be the diagnosis of progression according to RECIST. Responding patients without progression will be censored at their last tumor assessment showing response. Patients who never responded will be excluded from this analysis.
SD duration	Duration of SD will be analyzed using Kaplan-Meier methods. The starting point is the first study treatment administration. A patient who experiences any form of progression will be evaluated as a patient with event. The time point of the event will be the diagnosis of progression according to RECIST (PD) or iRECIST (iCPD). Patients without progression will be censored at their last tumor assessment showing response or any other best overall response except PD/iCPD.
PFS	PFS will be analyzed using Kaplan-Meier methods. A patient who experiences any form of progression or who

	dies of any cause will be evaluated as a patient with event.		
	The time point of the event will be the diagnosis of the		
	first progression according to RECIST/iRECIST or the		
	date of death. Patients without progression and still alive		
	will be censored at their last tumor assessment.		
OS	OS will be analyzed using Kaplan-Meier methods. Death		
	by any cause will be evaluated as event. Patients who are		
	still alive when they discontinue the study will be		
	censored at their last recorded date of being alive.		
Disease control rate	The number and percentage of patients with		
	SD/confirmed SD (iSD) per modified RECIST		
	v1.1/iRECIST or PR/iPR or CR/iCR will be displayed		
	per tumor assessment timepoint.		

Exploratory endpoints will be analyzed descriptively. Further details will be provided in the SAP.

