# Appendix 4 iRECIST

Response and progression will be evaluated in this study using the international criteria proposed by the revised RECIST v1.1 guideline (Eisenhauer et al., 2009) and according to iRECIST (Seymore et al., 2017), which introduces additional tumor assessments and evaluation criteria in situations where pseudo-progression is suspected.

This appendix describes the iRECIST process for assessment and evaluation of disease progression.

Tumor Assessment at Screening and Prior to iRECIST Progression

At every tumor assessment, target and non-target lesions identified at baseline by RECIST v1.1 will be assessed according RECIST v1.1. Until first radiographically assessed disease progression based on RECIST v1.1, there is no distinct iRECIST assessment. Accordingly, possible response evaluation outcomes are CR, PR, SD, PD, and not evaluable.

Response Evaluation and Decision at RECIST v1.1 Progression

At first radiographic assessment of disease progression according to RECIST v1.1, new lesions will be classified as measurable or non-measurable, using the same size thresholds and rules as for baseline lesion assessment in RECIST v1.1. From measurable new lesions,  $\leq$ 5 lesions total ( $\leq$ 2 per organ), may be selected as New Lesions – Target. The sum of diameters of these lesions will be calculated and kept distinct from the sum of diameters for target lesions at baseline. All other new lesions will be followed qualitatively as New Lesions – Non-target.

For patients whose radiological tumor assessment show evidence of disease progression by RECIST v1.1 criteria, the investigator will decide whether to continue a patient on study treatment and repeat imaging according to iRECIST or discontinue the patient according to disease progression according to RECIST v1.1. This decision by the investigator should be based on the patient's overall clinical condition, in particular in the assessment of clinical stability.

[figure not shown]
Clinical stability is defined as the following:

- No decline in ECOG PS
- Absence of increases of clinically relevant disease-related symptoms and signs assessed to be associated with disease progression
- No requirements for intensified management of disease-related symptoms, including increased analgesia, radiation, or other palliative care

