Any patient deemed **clinically unstable** should be discontinued from study treatment at site-assessed first radiologic evidence of disease progression and assigned a response evaluation of PD (according to RECIST v1.1), and it is not required to have repeat tumor imaging for confirmation of PD by iRECIST (iCPD).

If the patient is deemed to be clinically stable, and the investigator decides to continue treatment, new response categories defined by iRECIST, including iUPD and iCPD, will be used from there on (using iRECIST for patient management as shown in the figure below).

RECIST v1.1 and iRECIST: An Example of Assessment

iCR=complete response; iCPD=confirmed progression; iPR=partial response; iSD=stable disease; iUPD=unconfirmed progression; RECIST=Response Evaluation Criteria in Solid Tumors; TP=timepoint.

Note: Prefix "i" indicates immune responses assigned using iRECIST; others without "i" are confirmed by RECIST v1.1.

Source: Seymore et al., 2017

Additional imaging for confirmation should be scheduled 4 to 8 weeks from the imaging on which iUPD is seen. This may correspond to the next visit in the original visit schedule. Images should continue to be sent to the central imaging vendor for potential retrospective independent response evaluation

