#### Resolution of iUPD

Progression is considered not confirmed, and the overall response becomes iSD/iPR/iCR, if:

- None of the progression-confirming factors identified above occurs, AND
- The target lesion sum of diameters (initial target lesions) is not above the initial PD threshold.

The response is classified as iSD or iPR (depending on the sum of diameters of the target lesions), or iCR if all lesions resolve.

In this case (iSD, iPR, or iCR could be assigned), the initial iUPD is considered to be pseudo progression, and the level of suspicion for progression is 'reset'. This means that the next visit that shows radiographic progression, whenever it occurs, is again classified as iUPD by iRECIST, and the confirmation process is repeated before a response of iCPD- can be assigned.

Detection of Progression at Visits After Pseudo-progression Resolves

After resolution of pseudo-progression (i.e., achievement of iSD/iPR/iCR), iUPD is indicated by any of the following events:

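### Duration of response ends at RECIST progression, which for patients whose first response is iPR or iCR falls before the response begins; the stable-disease row uses a different event and the PFS row is unclear.

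*Combined protocol and SAP*

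**What the plan says.** The secondary-endpoint table in section 10.3.1 has three rows that depend on progression.

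- **Duration of response.** "The starting point is the first diagnosis of CR/iCR or PR/iPR". On who has an event: "A responding patient who experiences any form of progression will be evaluated as a patient with event". On the date: "The time point of the event will be the diagnosis of progression according to RECIST". Responders without progression are censored at the last assessment that shows response.
- **SD duration.** The clock starts at first study treatment. "The time point of the event will be the diagnosis of progression according to RECIST (PD) or iRECIST (iCPD").
- **PFS.** The event date is the "first progression according to RECIST/iRECIST or the" date of death.

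Appendix 4 sets the order in which categories can arise: "Until first radiographically assessed disease progression based on RECIST v1.1, there is no distinct iRECIST assessment". If the patient is clinically stable and treatment continues after that progression, "new response categories defined by iRECIST, including iUPD and iCPD, will be used from there on". If a later scan then gives iSD, iPR or iCR, "the initial iUPD is considered to be pseudo progression", and the suspicion of progression is reset.

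The plan expects such patients. Section 7.2.4 allows treatment past an initial RECIST PD with sponsor agreement. Examples 1 to 3 in the Appendix 4 table start at iUPD and end with a best response of iCR or iPR. Section 10.3.1 counts iCR and iPR towards the final criterion of more than 3 responders in 29.

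**The concern.** An iRECIST response is by construction a response after RECIST progression. If the response interval is closed by RECIST progression, with nothing saying that it must be a later one, a patient who enters the responder count through iPR or iCR has an interval that closes before it opens. The phrase about any form of progression does not help. On its plain wording the earlier PD makes the patient an event patient, so the censoring rule cannot apply even while the iPR is ongoing.

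A patient could then be a success on the primary endpoint and have a negative or undefined value on a named secondary endpoint. Someone would have to choose a rule at analysis, in an open-label trial, with the response sequences already known. The SD-duration row names a different event from the duration-of-response row, so the two could not be read together for patients followed under iRECIST.

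**Working it through.** No stated figure depends on these definitions. As background, the Simon design reproduces: early termination under p0 is 0.95^10 = 59.87% (stated 59.9%), type I error 4.68% (4.7%), type II error 19.89% (19.9%), and expected size 10 + (1 - 0.5987) × 19 = 17.6 (about 18). None of these uses the progression date.

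**Inputs.** Cycle 1 lasts 49 days and later cycles 42 days (section 7.2.1.1). Tumor assessments fall on Day 1 of each cycle from Cycle 2 (Appendix 1). On-schedule assessments are therefore on study days 50, 92, 134, 176, 218 and 260. The response sequences below are assumed for illustration; the documents give none.

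**Formula.** Duration = event day - day of first CR, iCR, PR or iPR.

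**Patient 1, first response is iPR:** iUPD day 50, iPR days 92 and 134, iUPD day 176, iCPD day 218. The start is day 92.

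**Patient 2, first response is PR:** PR day 50, iUPD day 92, iPR days 134 and 176, iUPD day 218, iCPD day 260. The start is day 50.

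| Event used | Patient 1 | Patient 2 |
|---|---|---|
| First RECIST PD (literal wording) | 50 - 92 = -42 days | 92 - 50 = 42 days |
| The iUPD that was later confirmed | 176 - 92 = 84 days | 218 - 50 = 168 days |
| iCPD | 218 - 92 = 126 days | 260 - 50 = 210 days |

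If Patient 1 instead stays in iPR through day 260, the literal result is unchanged: a RECIST PD is on record at day 50, so the patient is an event at -42 days rather than censored at day 260.

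The -42 days is one assessment interval. Appendix 4 places the confirmation scan 4 to 8 weeks after iUPD, so a first iPR at that scan gives -28 to -56 days. A later first iPR gives a more negative value.

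**Other rows, Patient 1.** SD duration could end on day 50 (PD) or day 218 (iCPD), and the row does not say which prevails. PFS ends on day 50 if the first RECIST PD counts. If the row means PD or iCPD according to how the patient was followed, PFS ends on day 218. The wording allows both.

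**The case against.** - **A sensible reading avoids the negative value.** Progression in a responding patient most naturally means progression after the response has begun, and Appendix 4 reclassifies the earlier PD as pseudo-progression. This is probably what was meant. But the dating sentence does not say it, and it leaves open whether a new iUPD or the iCPD ends the response (84 or 126 days for Patient 1).
- **PD/iCPD is a coherent shorthand.** Unstable patients are assigned PD and stable ones go on to iCPD, and several sections use the pair in that way. This supports the SD-duration row, and a similar reading of PFS is possible. It also shows what the duration-of-response row lacks.
- **Section 10.3 leaves exact definitions to the SAP.** It does, so it cannot be said that no definition will exist. The combined document supplies none beyond section 10, and a SAP that follows the rule already stated would inherit the conflict.
- **iCR and iPR may mean confirmed CR and PR.** The synopsis endpoint list and section 4.2.1 gloss them so, and on that gloss the problem disappears. The abbreviation list and Appendix 4 define them as iRECIST categories, so the gloss is a second inconsistency to settle.

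A reader might infer that every iPR or iCR responder is affected by a negative duration. Patient 2 shows otherwise: after an earlier PR the sign is right and only the length is in doubt.

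**Conclusion.** The point holds for patients whose first response is iPR or iCR: applied literally, the stated rule puts the event before the start of response and blocks censoring. For patients with PR, then iUPD, then iPR, the duration is positive but depends on the event (42 days by the literal rule, 210 days to iCPD in the example). The duration-of-response and SD-duration rows do not match, and the PFS row does not say whether a resolved first PD counts.

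Two further inferences are not supported. The first is that the three endpoints date one patient's progression in three ways. On the literal reading, duration of response and PFS both fall on the first RECIST PD (day 50 for Patient 1), and for patients never followed under iRECIST all three rows give the same PD date, apart from deaths in PFS. The second is a figure for how many patients are affected. At the threshold of 4 responders, one such patient would be 1/4 = 25% of the duration-of-response set, but that patient is hypothetical; the documents give no frequency of pseudo-progression.

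The impact is confined to descriptive secondary endpoints. ORR, the Simon boundaries and the sample size are unaffected. The day counts rest on on-schedule assessments and assumed response sequences. The wording should be corrected before the data are analysed.

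**What to change.** - **Duration of response.** Make the event the first progression after the first response. Define it as RECIST PD or, for patients followed under iRECIST, progression that is confirmed (iCPD) or never resolved. State one date convention, for example the date of the iUPD that was later confirmed. Say that a PD or iUPD that resolved to iSD, iPR or iCR is not an event. With that convention Patient 1 has 84 days and Patient 2 has 168 days.
- **SD duration.** Use the same definition of progression and the same date convention.
- **PFS.** State whether the first RECIST v1.1 PD or the iRECIST-based date is primary, and report the other as a sensitivity analysis. The documents do not require PFS to share the duration-of-response event, so this is a choice for the sponsor to declare.
- **Terminology.** Reconcile the confirmed CR/PR gloss of iCR and iPR in the synopsis and section 4.2.1 with Appendix 4 and the abbreviation list.

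The cost is revised wording in section 10.3.1, the synopsis, section 4.2.1 and the SAP, plus one derived date. No new data are needed.

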# **10.3.** Statistical Analyses

The statistical analysis plan (SAP) will be developed and finalized before the first patient is enrolled. The SAP will include the exact definition of endpoints and variables to be analyzed, extensive details on the statistical analysis methods to be used together with the structure of tables and figures to be included as end-of-text tables and figures as well as appended listings for the clinical study report. It will also describe procedures for accounting for missing, unused, and spurious data. This section is a summary of the planned statistical analyses of the primary and secondary endpoints.

Individual data will be listed. Data will be summarized using suitable descriptive statistics; depending on the structure of the data, summary statistics (e.g., number of observations, mean, standard deviation, minimum, median, maximum, lower quartile, upper quartile) or frequency tables may be used.

All data will be displayed by treatment arm if not specified otherwise.

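### Duration of response counts only progression as an event, so a responder who dies without documented progression is censored, which can overstate the duration

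*Combined protocol and SAP*

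**What the plan says.** The secondary-endpoint table in Section 10.3.1 analyses DoR by Kaplan-Meier methods in patients who reach at least PR/iPR, starting at the first diagnosis of response. The event rule is: "A responding patient who experiences any form of progression will be evaluated as a patient with event". The only event date given is the diagnosis of progression. The censoring rule is: "Responding patients without progression will be censored at their last tumor assessment showing response". The row does not mention death and does not call the endpoint time to progression.

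In the PFS row of the same table, a patient who "dies of any cause will be evaluated as a patient with event", and the date of death can be the event date. Censoring there is limited: "Patients without progression and still alive" are the only patients censored, at their last tumor assessment.

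Section 10.3 describes itself as a summary of the planned analyses and defers detail: "The SAP will include the exact definition of endpoints and variables to be analyzed". The document as supplied contains no SAP section that adds death to the DoR rule.

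**The concern.** Take a responder whose last scan still shows response and who dies before the next one. For PFS this patient has an event on the date of death. For DoR the same patient is censored at the scan. Kaplan-Meier censoring treats the patient as still at risk of progression, with the same outlook as responders who remain alive. A dead patient has no such outlook, and the response has in fact ended. The curve hands this patient's weight to the survivors, so the median tends to come out longer.

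Such deaths are possible under the visit schedule. Scans are about 6 weeks apart on treatment. They can be 12 weeks apart after the EOT Visit (Section 5.4.2) or once a response has lasted a year (Section 8.2). With few responders per arm, one such death can move the median. In a study judged on response rate, DoR tells the reader whether the responses last, and this error runs in the product's favor.

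**Working it through.** **The plan's own figures.** Section 10.1 gives 10 + 19 = 29 patients, p0 = 5%, p1 = 20%, a stop at 0 responders of 10, and rejection at more than 3 of 29. Exact binomial calculation returns a type I error of 0.0468 (stated 4.7%), type II error 0.1989 (19.9%), early termination 0.5987 (59.9%) and an expected sample size of 17.6 (about 18). All agree, and none depends on the DoR rule. The documents give no figure for DoR itself.

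**1. Effect on the median.** Let λp and λd be constant hazards of progression and of death without progression during response, and s = λd/(λp + λd).

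- Median with deaths counted: ln 2/(λp + λd).
- Median with deaths censored: ln 2/λp.
- Ratio: 1/(1 − s), which is 1.00, 1.11, 1.25 and 1.43 at s = 0, 10%, 20% and 30%.

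The range of s is assumed. For example, a 12-month median with deaths censored corresponds to 12 × 0.8 = 9.6 months with deaths counted at s = 20%.

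**2. Expected responders at a 20% response rate.** The chance of 0 of 10, which stops the arm, is 0.8^10 = 0.107. The mean is 10 × 0.2 + (1 − 0.107) × 19 × 0.2 = 5.4. Given that Stage 2 is reached it is 5.4/0.893 = 6.0. This treats response at the interim analysis as final response.

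**3. Chance of at least one affected responder.** Let f be the share of responses that end under observation. Each patient is an affected responder with probability p·s·f, so

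P = 1 − (1 − p)^10 − [(1 − psf)^10 − (1 − p)^10] × (1 − psf)^19.

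At p = 0.2, s = 0.2, f = 1: 1 − 0.107 − (0.665 − 0.107) × 0.460 = 0.636.

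| s | P, f = 1 | P, f = 0.5 | Median changes, f = 1 | Median changes, f = 0.5 |
|---|---|---|---|---|
| 10% | 41% | 23% | 21% | 11% |
| 20% | 64% | 41% | 38% | 21% |
| 30% | 76% | 54% | 52% | 31% |

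The last two columns come from 20,000 simulated trials per setting, with the Stage 1 stop, exponential DoR with an assumed median of 9 months, and deaths censored at the last 6-weekly scan. For f = 0.5 the other-censoring hazard equals the event hazard. A change includes a median that is no longer reached. At least 97% of changes are upward or to not reached.

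At the null rate of 5%, the same formula with f = 1 gives 8%, 15% and 21%.

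**4. A hand example (invented data).** Six responses end at 3, 5, 7, 9, 11 and 13 months. With all counted, survival falls to 3/6 at month 7, so the median is 7. Suppose the 5-month event is a death, censored at a scan at 3.6 months. Survival is then 5/6 at month 3, 5/6 × 3/4 = 0.625 at month 7 and 0.625 × 2/3 = 0.417 at month 9, so the median is 9. If the 9-month event is the death instead, the median stays at 7.

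**The case against.** The strongest reply is that the final definition is not visible. Section 10.3 calls itself a summary and leaves exact definitions to the SAP. That limits what can be said about the rule finally applied. It does not answer the point, because the row is not silent: it states an event, a date and a censoring rule. A SAP that follows it keeps the problem, and one that departs from it contradicts the protocol.

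A second reply is that a progression-only rule is coherent as time to progression. That is fair, but the endpoint is not labelled that way.

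Third, the harm is limited. Section 8.2.1 calls for imaging whenever progression is suspected, PFS and OS count every death, and individual data will be listed. All of this stands and lowers the importance of the point. It does not correct the reported DoR curve.

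Some stronger readings are tempting but not supported:

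- **That DoR will be overstated.** The effect is zero if no responder dies without documented progression. The median OS below one year in Section 3.1 describes patients who do not respond to cemiplimab. It says nothing on s among responders here.
- **That 29 × 0.20 = 5.8 responders should be expected.** This ignores the Stage 1 stop in Section 10.3.4.1.
- **That the dating words are a second bias.** The DoR row dates progression by RECIST, while the PFS row uses the "first progression according to RECIST/iRECIST or the" date of death. No effect of this difference has been shown, and the endpoint wording in Section 4.2.1.1 allows more than one reading. It is a wording inconsistency.
- **That SD duration is equally wrong.** Its row also omits death, but no effect has been worked out for that endpoint, and it is not part of this point.

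**Conclusion.** The concern holds for the rule as written in Section 10.3.1. A responder who dies without documented progression is censored for DoR and is an event for PFS, and this can overstate DoR. Whether the SAP keeps the rule cannot be judged from the supplied text.

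The size is conditional. Median inflation of 11% to 43% needs constant hazards and an assumed s of 10% to 30%. The chance that an arm is affected at all also needs a 20% response rate and an assumed f, and is smaller at lower response rates. The simulated shares of changed medians further assume exponential DoR with a 9-month median. With half the responses censored for other reasons, about half of the changed medians at s of 20% to 30% become not reached, so those are not a measured lengthening.

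DoR is a descriptive secondary endpoint. The response-rate analysis, the two-stage decision rule, PFS and OS do not depend on it. The rule should be corrected before results are known, but it does not threaten the trial's main conclusion.

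**What to change.** - Define the DoR event as the earlier of first progression after the start of response and death from any cause.
- Censor only responders who are alive without progression, at their last evaluable tumor assessment, in line with the PFS row.
- State, identically for DoR and PFS, how a death after new antineoplastic therapy or after missed scans is handled. Under Section 5.4.2 tumor assessments stop at new therapy while survival follow-up continues, so counting every late death at its own date could itself lengthen DoR.
- If time to progression is what is wanted, label it so and report DoR with death counted beside it.

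The cost is a few sentences in the protocol table and the SAP. Survival status and deaths are already collected (Sections 5.4.2, 8.3.7 and 9.4). Section 8.3.7 foresees an unknown date of death, so a convention for that case belongs in the same text. The reported median DoR may become shorter: under constant hazards by the share s, which is 0% to 30% over the assumed range.

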#### **Response Criteria**

#### **Evaluation of Target Lesions**

- **CR:** Disappearance of all target lesions. Any pathological lymph nodes (whether target or non-target) must have reduction in short axis to <10 mm (<1 cm).
- **PR**: ≥30% decrease in the sum of the diameters of target lesions, taking as reference the baseline sum diameters

- **PD:** ≥20% increase in the sum of the diameters of target lesions, taking as reference the smallest sum on study (this includes the baseline sum if that is the smallest on study). In addition to the relative increase of 20%, the sum must also demonstrate an absolute increase of ≥5 mm (0.5 cm).
  - Note: The appearance of  $\geq 1$  new lesion is also considered progression.
- **SD:** Neither sufficient shrinkage to qualify for PR nor sufficient increase to qualify for PD, taking as reference the smallest sum diameters while on study

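### Duration of response is censored at the last assessment still showing response although only progression is an event, so observed progression-free time after a PR-to-SD drift is discarded informatively

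*Combined protocol and SAP*

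**What the plan says.** The secondary-endpoint table in Section 10.3.1 sets three rules for duration of response.

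- Population and method: "Duration of response will be analyzed for patients who reach at least PR/iPR at any time during the study using Kaplan-Meier methods".
- Event: "A responding patient who experiences any form of progression will be evaluated as a patient with event". On its date: "The time point of the event will be the diagnosis of progression according to RECIST".
- Censoring: "Responding patients without progression will be censored at their last tumor assessment showing response".

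The row label spells out response as CR/iCR/PR/iPR. Two neighbouring rows use different censoring dates. For SD duration: "Patients without progression will be censored at their last tumor assessment showing response or any other best overall response except PD/iCPD". For PFS, patients alive without progression "will be censored at their last tumor assessment". Unlike the PFS row, the response-duration row does not count death as an event.

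In Appendix 3 (Evaluation of Target Lesions), PR is a "≥30% decrease in the sum of the diameters of target lesions" relative to baseline. PD is a rise of at least 20% and at least 5 mm over the smallest sum on study. SD is "Neither sufficient shrinkage to qualify for PR nor sufficient increase to qualify for PD".

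**The concern.** Because progression is the event, a responder remains at risk until PD, whatever the category in between. The censoring date stops earlier, at the last visit in response. The two dates part company for one kind of patient: a responder whose tumor sum rises back above the PR cut-off without reaching PD and who has not progressed by the last scan.

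That patient's later scans are scheduled and read. Section 8.2 asks for assessment after every cycle, and Section 5.4.2 for assessment every 12 weeks after treatment stops without progression. Those scans show no progression, and the rule drops them. If the same patient progresses later, the whole interval counts. How long a drifting patient stays in the risk set is therefore decided by what happens afterwards, which breaks the non-informative censoring that Kaplan-Meier needs. At stake is the reported duration of response in arms where few responders are expected.

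**Working it through.** **1. Plan's own figures.** The documents give no figure for duration of response. The Simon design in Section 10.1 reproduces: for 0/10 then 3/29 with p0 = 5% and p1 = 20%, type I error is 0.0468, type II error 0.1989, early termination 0.5987 and expected size 17.6. At the design alternative an arm yields 29 × 0.20 = 5.8 responders.

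**2. Can a responder become SD without PD?** Let B be the baseline sum and N the nadir. PR requires a sum of at most 0.70B. PD requires a sum of at least max(1.2N, N + 5 mm). There is an SD gap when the PD threshold lies above 0.70B.

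- Percentage rule: 1.2N > 0.70B, so N > 0.70/1.2 = 58.3% of B. A nadir of 58.3% to 70% of baseline leaves a gap. Example: B = 100 mm, N = 65 mm, now 75 mm. The PR cut-off is 70 and the PD cut-off 78, so the visit is SD.
- 5 mm rule for small sums: N > 0.70B − 5. For B = 30 mm, N > 16 mm (53.3%); for B = 20 mm, N > 9 mm (45%).
- Bi-dimensional criteria in Appendix 3 (50% decrease, 25% increase): if the increase is taken from the nadir, which that text does not state, the gap is 50/1.25 = 40% to 50% of baseline.

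**3. Direction.** The rule leaves every event time unchanged and moves some censoring times earlier. Each Kaplan-Meier factor is 1 − d/n, with the same d and an equal or smaller n. The curve is therefore equal or lower at every time.

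**4. A six-responder example (assumed data).** PD at 4, 7 and 10 months; three responders progression-free at 12 months. Two of these drifted to SD and last showed response at 3 and 6 months.

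| Censoring | S(4) | S(7) | S(10) |
|---|---|---|---|
| Last non-PD scan | 5/6 = 0.83 | × 4/5 = 0.67 | × 3/4 = 0.50 |
| As written, one drifter (last response month 3) | 4/5 = 0.80 | × 3/4 = 0.60 | × 2/3 = 0.40 |
| As written, two drifters | 4/5 = 0.80 | × 2/3 = 0.53 | × 1/2 = 0.27 |

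The median stays at 10 months with two drifters; the landmark rates move.

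**5. Average size (all inputs assumed).** Time to PD is the sum of two exponential phases, with mean 26 weeks and then 26 or 39 weeks. Scans are 6-weekly and follow-up is uniform over 12 to 104 weeks. A stated share of responders spends the second phase in SD; the rest stay in PR until PD. Entries are 52-week rates, last non-PD scan versus as written.

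| Share drifting | 26 then 26 weeks | 26 then 39 weeks |
|---|---|---|
| 10% | 45.0% vs 44.3% | 56.0% vs 55.1% |
| 30% | 45.0% vs 42.8% | 56.2% vs 53.2% |
| 100% | 44.9% vs 36.6% | 56.0% vs 44.1% |

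With a short SD phase (52 then 13 weeks), even 100% drift gives 52.1% vs 50.4%.

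Longer follow-up (assumed 125 to 145 weeks, 20% dropout per year; 26 then 26 weeks) gives 44.7% vs 42.2% at 100% drift and 44.8% vs 44.1% at 30%. Without dropout, 100% drift gives 45.0% vs 44.5%.

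A second model used a single exponential time to PD with median 6, 12 or 18 months, follow-up of 6 to 24 months, and 10% to 50% of responders drifting. It puts the 12-month loss at about 0.1 to 1.6 points and the change in median at zero to one visit.

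**The case against.** **Size.** Losses of 8 to 12 points appear only when every responder drifts, and nothing in the documents supports that. Drift needs a shallow response or a small tumor sum. Deeper responders reach the PD threshold before losing PR, and new lesions are PD outright. Treatment runs to about 2 years with 12 months of follow-up, so many drifters will have progressed by the last scan and be unaffected. This stands, and it limits the expected average effect to a few points at most unless drift is common.

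**Direction.** A reader might infer that the reported duration of response will be too short overall. The documents do not support that. The same row omits death as an event, which pushes the estimate upward, and the net direction is unknown. A reader might also infer that late risk sets hold only patients who will progress. They do not: responders still in CR or PR at their last scan stay at risk up to that scan.

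**Deferral to the SAP.** Section 10.3 calls its text a summary and leaves exact endpoint definitions to the SAP. The rule may be refined there, but nothing in the supplied text does so, and the protocol states a specific rule rather than leaving a gap.

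**Benign wording.** One could read the censoring phrase as covering any non-PD visit. The SD-duration row tells against this: it mentions response and then adds the other non-PD categories separately.

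**Consequence.** The endpoint is secondary and descriptive, and sampling error with about six responders exceeds the average shifts. That lowers the stakes but does not make the rule coherent.

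**Conclusion.** The point holds for the censoring rule. It discards progression-free time that was observed, does so according to later outcome, and conflicts with the SD-duration and PFS rows. Its effect taken alone can only be to lower the curve; this follows from the risk sets and needs no simulation. A net downward bias of the duration-of-response estimate is not shown.

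The size rests on an unknown drift fraction and on assumed times and follow-up: about 1 point on the 52-week rate at 10% drift and 2 to 3 points at 30%, with 8 to 12 points as the extreme case. In a single arm of about six responders the shift can be larger, as the example shows. ORR, PFS, OS and the Simon decisions do not change.

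**What to change.** Replace the censoring sentence in the response-duration row of Section 10.3.1, and carry the same text into the SAP: responders who have not progressed are censored at their last evaluable tumor assessment not showing PD/iCPD. This agrees with the PFS row.

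If time spent in response is what is wanted, loss of response must be made an event instead; progression as the event with loss of response as the censoring date is not a coherent pair.

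The cost is one sentence. The scans are already scheduled, and no sample size, visit or decision rule changes.
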